10.2 Patient demographics/other baseline characteristics

Continuous variables will be summarized by sample size, mean, standard deviation, median, minimum, and maximum. Discrete variables will be summarized by frequencies and percentages.

10.3 Treatments (study drug, other concomitant therapies, compliance)

The average daily dose of tacrolimus extended-release will be summarized within defined time windows. These summaries will apply the following rule: On calculating dosage averages over a time period, zero doses will be used for periods of temporary interruption of study medication regardless of whether this was due to safety reasons, non-compliance or other reasons. The reasons for tacrolimus extended-release dose adjustments will be assessed at these time points. Other immunosuppressive medication will be summarized by WHO drug names. All non-immunosuppressive medications or non-drug therapies will be grouped into prior medications and concomitant medications.

10.4 Analysis of the primary objective(s)

10.4.1 Variable

The primary objective is treatment failure at one year post transplant. Treatment failure is defined as a composite of biopsy proven acute rejection (BPAR), graft failure, or death. BPAR is defined as \geq Banff 1A using the Banff 2007 criteria. Discrete variables will be summarized by frequencies and percentages. Serious adverse events will be summarized. Categorical variables will be analyzed by Chi square and continuous variables by T-test.

10.4.2 Safety

Safety variables to be assessed include discontinuation from study, discontinuation from treatment, renal function, SAEs, notable events, and laboratory tests. The number of serious adverse events will be reported as an observation since this is a pilot study. Safety data will be reviewed quarterly by a PI and designated Co-PIs.

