This is a single center, pilot trial. It will be an open label, single-arm, non-controlled design. All HS patients age 18 and older requiring desensitization may be included in the study. Twenty subjects will be enrolled in the study. Subjects will take part in the study until they are one-year post-transplant. All subjects will require informed consent. At the time of screening, subjects will receive a physical exam and undergo lab testing as detailed below in the evaluation schedule. Alemtuzumab (Campath 1H, Lemtrada) will be administered to all subjects for induction immunosuppression immediately post-transplant. Maintenance immunosuppression will consist of tacrolimus extended-release, mycophenolate mofetil, and prednisone. Patients will receive antimicrobial prophylaxis as per Cedars-Sinai Medical Center (CSMC) protocol (valganciclovir x 6 months, TMP/SMX x 12months, and fluconazole x 1 month). Lab tests and physical exams for safety will take place according to the evaluation schedule below. Safety will be assessed by the reporting of serious adverse events as described below. Tacrolimus extended-release trough level, complete metabolic panel, complete blood count with differential, donor specific antibodies, and urinalysis with culture will be assessed according to the evaluation schedule below. Subjects will complete the study at one year post-transplant. Consent may be withdrawn by the study participant at any time. The investigator may also withdraw the study participant at any time if there are any safety concerns.

Efficacy assessments:

This is a pilot study and no efficacy assessments will be made.

Data analysis:

All outcomes will be reported as frequencies. Safety will be assessed by measuring the frequency of serious adverse events at one year post transplant. The frequency of BPAR, graft loss, and death will also be assessed at one year post transplant.

1 Background

Kidney transplantation remains the gold standard for the treatment of end-stage kidney disease. Advances in immunosuppression are integral to the success of kidney transplantation. Current immunosuppression regimens have reduced the number of rejections. However, long-term allograft survival remains a challenge. One limitation of immunosuppression regimens is the pill burden placed upon the recipients. This leads to long-term non-adherence and late rejections that ultimately place the allograft at risk^[1,2].

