3.2 Secondary objectives

Secondary objectives are to observe the following:

1. Change in DSA as defined by the DSA relative intensity score (RIS) defined by: 0 points for no DSA, 2 points for each weak DSA (MFI <5,000), 5 points for each moderate DSA (MFI 5,000 -10,000), and 10 points for each strong DSA (MFI >10,000)^[1,2].
2. Tolerability as defined by the number of subjects discontinuing the study medication

4 Study design

The study will be a single center, pilot trial. It will be an open label, single-arm, non-controlled design. All HS kidney transplant recipients, age 18 and older, requiring desensitization may be included in the study. Initial desensitization protocol for LD or DD includes Intravenous Immunoglobulin (IVIG) 2g/kg (>70kg max 140g) given on day 0 (split over 2 days for peritoneal dialysis patients), rituximab 375mg/m² (rounded to the nearest 100mg vial) given on day 15, and IVIG 2g/kg (>70kg max 140g) given on day 30. Recipients for LD or DD who are unresponsive to IVIG/ritux (after 2 months for LD and after 6 months for DD) will require plasma exchange (PLEX) 5-7 sessions followed by IVIG 2g/kg (>70kg max 140g) and rituximab 375mg/m². Patients will be receiving acetaminophen, antihistamine, and steroid as premedication for all infusions.

A total of 20 subjects will be enrolled in the study. Subjects will take part in the study until they are one year post-transplant. All subjects will require informed consent. At the time of screening, subjects will receive a physical exam and undergo lab testing as detailed below in the evaluation schedule. Alemtuzumab (Campath 1H, Lemtrada) 30mg, will be administered subcutaneously to all subjects for induction immunosuppression immediately post-transplant. Maintenance immunosuppression will consist of tacrolimus extended-release, mycophenolate mofetil 500mg twice daily or mycophenolate sodium 360mg twice daily, and prednisone. Patients will receive antimicrobial prophylaxis per CSMC protocol. Lab tests and physical exams for safety will take place according to the evaluation schedule below. Safety will be assessed by the reporting of serious adverse events as described below.

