6.1.5 Permitted study drug dose adjustments and interruptions

Blood for tacrolimus extended-release trough levels will be obtained from all patients at the time points indicated in Flowchart of Procedures. Therapeutic drug monitoring will be mandatory for all patients throughout the study. For patients who are unable to tolerate the protocol-specified dosing scheme, dose adjustments and interruptions are permitted in order to keep the patient on study drug. PI will follow local practice guidelines for these adjustments and interruptions.

The first tacrolimus level should be drawn after two doses are administered. Tacrolimus extended-release dose adjustments should be made based on results of the trough levels from the local laboratory. Follow-up tacrolimus trough levels should be rechecked after any dose adjustments are made to ensure that the recommended troughs are achieved.

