8.1 Adverse events

An adverse event is the appearance or worsening of any undesirable sign, symptom, or medical condition occurring after starting the study drug even if the event is not considered to be related to study drug. Study drug includes the investigational drug under evaluation. Medical conditions/diseases present before starting study drug are only considered adverse events if they worsen after starting study drug. Abnormal laboratory values or test results constitute adverse events only if they induce clinical signs or symptoms, are considered clinically significant, or require therapy. The occurrence of adverse events should be sought by non-directive questioning of the patient at each visit during the study. Adverse events also may be detected when they are volunteered by the patient during or between visits or through physical examination, laboratory test, or other assessments.

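### Adverse events are sought at every visit, but the planned event analysis covers only SAEs and an undefined category, so symptomatic toxicity managed by dose change enters neither the SAE nor the tolerability count

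*Combined protocol and SAP*

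**What the plan says.** Collection is broad. Section 8.1 sets a definition that is not limited to serious events: "An adverse event is the appearance or worsening of any undesirable sign, symptom, or medical condition occurring after starting the study drug". It also says how often to look: "The occurrence of adverse events should be sought by non-directive questioning of the patient at each visit during the study". Table 2 marks adverse events from Day 0 through Month 12.

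The planned event analysis is narrower:

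- Synopsis, Data analysis: "Safety will be assessed by measuring the frequency of serious adverse events at one year post transplant". Section 4 likewise ties the safety assessment to SAE reporting.
- Section 10.4.1: "Serious adverse events will be summarized".
- Section 10.4.2: "Safety variables to be assessed include discontinuation from study, discontinuation from treatment, renal function, SAEs, notable events, and laboratory tests".

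Tolerability is a secondary objective (3.2): "Tolerability as defined by the number of subjects discontinuing the study medication". The glossary defines study drug discontinuation as a permanent stop.

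For patients who cannot tolerate the dosing scheme, section 6.1.5 says that "dose adjustments and interruptions are permitted in order to keep the patient on study drug". Section 10.3, on treatments, adds: "The reasons for tacrolimus extended-release dose adjustments will be assessed at these time points". It also enters temporary interruptions into the average dose as zeros, whatever their cause.

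**The concern.** This is a single-arm pilot of 20 patients with no efficacy assessment, so describing safety and tolerability is its main product. Common events are what 20 patients can describe best. The two event-based measures respond to severe outcomes: an event that meets the SAE definition, or a patient who stops for good. A symptom that is frequent, troublesome and not serious, and that is managed by lowering or pausing the dose, meets neither. Section 6.1.5 itself recognises this patient, someone unable to tolerate the dosing who nevertheless stays on drug, but the tolerability measure does not count that patient. The answer given to the tolerability question could then reflect how often sites managed to keep patients on drug more than how often the drug was hard to take.

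**Working it through.** The documents state no derived figure on this point (N = 20 has no calculation behind it), so there is nothing to reproduce. The check is mainly a comparison of text.

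**Step 1. Where would each kind of event appear in the planned report?**

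| Type of event | SAE count | Tolerability count | Elsewhere in section 10 |
|---|---|---|---|
| Meets the SAE definition (8.2) | Yes | Only if the drug is permanently stopped | – |
| Non-serious, drug permanently stopped | No | Yes | Discontinuation, 10.4.2 |
| Non-serious, seen in renal function or laboratory tests | No | No, if kept on drug | Yes, named in 10.4.2 |
| Non-serious, symptomatic, dose adjusted | No | No | Reason for adjustment, 10.3 |
| Non-serious, symptomatic, drug interrupted then resumed | No | No | Zero doses in the average, 10.3 |
| Non-serious, symptomatic, no dose action | No | No | Nothing named, unless treated as a 'notable event' |

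The last three rows are the gap. All three are recorded under 8.1, and none has a stated safety or tolerability analysis.

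**Step 2. Does 10.3 fill it?** Only partly. Doses are also adjusted routinely to reach trough targets (6.1.4, 6.1.5), and 10.3 does not plan a separate count of patients whose dose changed because of an adverse event. Interruptions are averaged as zeros without regard to cause. The output is a summary of exposure.

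**Step 3. Size, by illustration.** The event rate *p* and the share *k* of affected patients kept on drug are assumptions; neither is in the documents. The toxicity is assumed to be non-serious, and all 20 patients are assumed to start treatment.

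- Expected number affected = 20 × *p*
- Chance of seeing at least one case = 1 − (1 − *p*)^20
- Expected discontinuations counted = 20 × *p* × (1 − *k*)

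| *p* | Expected affected | Chance of ≥ 1 case | Counted, *k* = 50% | Counted, *k* = 80% | Counted, *k* = 100% |
|---|---|---|---|---|---|
| 20% | 4 | 0.989 | 2 | 0.8 | 0 |
| 30% | 6 | 0.999 | 3 | 1.2 | 0 |
| 50% | 10 | > 0.999 | 5 | 2 | 0 |

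For *p* = 30% and *k* = 80%: 20 × 0.30 = 6 affected, and 6 × 0.20 = 1.2 counted. The SAE count gains nothing in any cell, because the toxicity is assumed to be non-serious.

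**Step 4. What a by-patient table would show.** Exact (Clopper-Pearson) 95% intervals with n = 20:

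| Patients with the event | Exact 95% interval |
|---|---|
| 0/20 | 0 to 16.8% |
| 4/20 | 5.7 to 43.7% |
| 6/20 | 11.9 to 54.3% |
| 8/20 | 19.1 to 63.9% |
| 10/20 | 27.2 to 72.8% |

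The intervals are wide, but an event seen in 8 of 20 patients has a lower limit of 19.1%, which is information that the two present counts could miss.

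**The case against.** Several points on the other side stand and limit the claim.

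- **Exclusion.** A reader might infer that the plan excludes non-serious adverse events from analysis. It does not say so. The list in 10.4.2 is introduced as what the variables include, so it is open, and it holds a 'notable events' item separate from SAEs. The DSMB charter is an appendix whose text is not reproduced, so whether it defines the term is unknown. The fault is that the plan commits to nothing and leaves the choice of events until the data are in hand.
- **Coverage.** Renal function and laboratory tests are named safety variables, and the SAE definition in 8.2 reaches some medically significant events. The gap is therefore mainly symptomatic or clinical non-serious events.
- **Section 6.1.5.** A reader might infer that it instructs the site to keep intolerant patients on drug. It permits dose changes and interruptions under local practice guidelines, and nothing in it prevents stopping.
- **Section 10.3.** A reader might infer that toxicity managed by dose change would be invisible. Dose changes must be recorded (6.1.4) and their reasons assessed, so some of it would be seen, though as exposure data mixed with trough-driven changes.
- **Numbers.** The zero counts at *k* = 100% follow from the assumptions. They show what the measures cannot detect and say nothing about what will happen. Nor do the documents support a prediction that the report will call the drug well tolerated.

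It can also be argued that tolerability is consistently prespecified, so a second measure is a matter of preference. Discontinuation can stay as it is. But with 6.1.5 in force, it alone undercounts intolerance that the protocol itself recognises.

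**Conclusion.** The point holds in limited form. All adverse events are sought, yet every explicit event analysis is confined to SAEs plus an undefined category, and tolerability counts permanent stops only. Symptomatic, non-serious toxicity managed by a permitted dose change or interruption enters neither count. The size cannot be taken from the documents. Under assumed rates of 20% to 50%, with 50% to 100% of affected patients kept on drug, between 0 and 5 of an expected 4 to 10 affected patients would count as discontinuations and none as SAEs. The conclusion rests on reading discontinuation as the glossary defines it, and on 'notable events' having no definition in the text available. This is a reporting weakness that should be corrected. No existing figure is wrong, and no clinical management rule is in question.

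**What to change.** In 10.4.2:

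1. Define 'notable events', or delete the term.
2. Add a by-patient table of all recorded adverse events: n/20, percentage and exact 95% interval for each, with severity and investigator-assessed relatedness where collected.
3. Keep discontinuation as the tolerability measure and put a second one beside it: the number of patients with any adverse event leading to dose reduction, interruption or permanent stop. Count these separately from adjustments made only to reach trough targets.

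A row for CMV and BKV PCR positivity is optional. These tests sit under Safety in 7.3.5 but are not named in 10.4.2.

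The cost is small: some extra tabulation for 20 patients, mostly from data already recorded. Section 8.1 mentions no severity grading, and relatedness appears only for SAE reporting in 8.2, so the adverse event form may need fields for severity, relatedness and action taken. Relatedness should be read cautiously, since the trial has no control arm and every patient takes several other immunosuppressive drugs. The change affects reporting only.

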10.5 Sample size calculation

This is a pilot study therefore sample size calculation is not applicable. Twenty

patients will be enrolled.

11 Ethical considerations

11.1 Regulatory and ethical compliance

This clinical study was designed and shall be implemented and reported in accordance with the ICH Harmonized Tripartite Guidelines for Good Clinical Practice, with applicable local regulations (including European Directive 2001/20/EC, US Code of Federal Regulations Title 21, and Japanese Ministry of Health, Labor, and Welfare), and with the ethical principles laid down in the Declaration of Helsinki.

11.2 Informed consent procedures

Eligible patients may only be included in the study after providing written (witnessed, where required by law or regulation), IRB/IEC/REB-approved informed consent, or, if incapable of doing so, after such consent has been provided by a legally acceptable representative of the patient. In cases where the patient's representative gives consent, the patient should be informed about the study to the extent possible given his/her understanding. If the patient is capable of doing so, he/she should indicate assent by personally signing and dating the written informed consent document or a separate assent form. Informed consent must be obtained before conducting any study-specific procedures (i.e. all of the procedures described in the protocol). The process of obtaining informed consent should be documented in the patient source documents.

Women of child bearing potential should be informed that taking the study medication may involve unknown risks to the fetus if pregnancy were to occur during the study and agree that in order to participate in the study they must adhere to the contraception requirement for the duration of the study and 8 weeks after study drug discontinuation. If there is any question that the patient will not reliably comply, they should not be entered in the study.

11.3 Responsibilities of the investigator and IRB/IEC/REB

The protocol and the proposed informed consent form must be reviewed and approved by a properly constituted Institutional Review Board/Independent Ethics Committee/Research Ethics Board (IRB/IEC/REB) before study start. A signed and dated statement that the protocol and informed consent have been approved by the IRB/IEC/REB must be given to Astellas before study initiation.

11.4 Publication of study protocol and results

The results of this trial will be submitted for publication upon completion of the trial and after all data have been analyzed. The study protocol will be summarized as part of the submission.

12 Protocol adherence

